10.4 RANDOMIZATION AND MASKING

A randomization list will be created by the JJSV biostatistician for each investigative site and the randomization code will be uploaded into the electronic data capture system (EDC). [REDACTED]

[REDACTED]

As part of the informed consent process, the investigator or delegate will explain to the subject the requirements of a randomized study and the differences expected between the two lens models in the study: TECNIS Eyhance lens and the control lens. [REDACTED]

[REDACTED]

The subjects and the study technicians performing the postoperative vision tests are to be masked through study completion. [REDACTED]

[REDACTED]

[REDACTED] Following completion of the final study exam, each subject will be given the permanent IOL implant identification card.

10.5 STUDY LENS SUPPLY

[REDACTED]
[REDACTED] Sites will follow their respective procedures for storage, access, and use of intraocular lenses, and accountability for implanted study lenses must be documented (See Section 15.2 Lens Accountability).

10.6 OPERATIVE PROCEDURES

The investigator should use his or her standard, small-incision, cataract extraction surgical technique using the preloaded system or one of the JJSV-validated insertion systems described in Section 7.2.

[REDACTED]

[REDACTED]

Operative case report forms will include the following information:

INCISION TYPE AND SIZE

Lenses should be inserted through an incision ranging in size from approximately 2.2-3.0 mm, per the investigator's standard technique. The incision may be clear corneal, limbal or scleral tunnel at the discretion of the investigator.

CAPSULORHEXIS SIZE AND METHOD

The anterior capsulotomy should be a continuous, curvilinear capsulorhexis approximately 5.0 to 5.5 mm in diameter to allow slight overlap of the lens optic edge.

[REDACTED]

LENS REMOVAL

Lens removal may occur using laser fragmentation combined with phacoemulsification/aspiration or using only phacoemulsification/aspiration.

VISCOELASTIC

Viscoelastic materials should be used as is customary for each investigator and recorded on the case report form (CRF).

IMPLANT INSTRUMENTATION USED

TECNIS 1-Piece Model ZCB00 lenses should be folded for implantation and inserted into the capsular bag [REDACTED]

[REDACTED]

SURGICAL COMPLICATIONS

Should a surgical complication occur, implantation of a study lens will be at the investigator’s discretion. In the event of capsular bag or zonular rupture, the lens should not be implanted if the complication may result in lens instability. Additionally, the lens is not to be implanted in the sulcus. [REDACTED]

[REDACTED]

MEDICATIONS

Preoperative, operative, and intraoperative medications should be used as is customary for each investigator and will be recorded in source and on the CRF.

TYPE OF CLOSURE

Wound closure is left to the surgeon’s discretion and will be recorded on the CRF.

ADDITIONAL OPERATIVE INFORMATION COLLECTED INCLUDES:

- Date of surgery
- Operative eye
- Lens power and serial number
- Lens placement
- [REDACTED]
- Surgical technique according to protocol
- Product complaints
- Serious and/or device-related adverse events

10.7 POSTOPERATIVE PROCEDURES

Postoperatively, subjects will be examined according to the schedule in Section 10.2, Visit Schedule. [REDACTED]

Study technicians responsible for conducting all vision testing will be masked.

[REDACTED]

[REDACTED]
[REDACTED].

[REDACTED]
[REDACTED]
[REDACTED]
[REDACTED]

A postoperative CRF will collect the following information, although not all data are required at every visit (see **Appendix A**):

MANIFEST REFRACTION [REDACTED]
[REDACTED]

Postoperative study manifest refractions are to be performed [REDACTED]
[REDACTED]. Manifest refraction (MR) is to be performed [REDACTED]
[REDACTED] as detailed in **Appendix C**.

[REDACTED]
[REDACTED]
[REDACTED]
[REDACTED]

DISTANCE VISUAL ACUITY TESTING (MASKED PROCEDURE)

Distance visual acuity will be measured postoperatively under photopic lighting conditions (85 cd/m², 80–110 cd/m² acceptable) [REDACTED]
[REDACTED]
[REDACTED].

Instructions for [REDACTED] are detailed in **Appendix E**, and for distance visual acuity in **Appendix F**.

The following distance visual acuity measurements are to be performed per the visit schedule in **Appendix A**:

| Test | Test Distance | Illumination | Type of Testing | [REDACTED] [REDACTED] |
|-------|---------------|----------------------------------|----------------------|--------------------------|
| UCDVA | 4 m | Photopic (85 cd/m ²) | Monocular, Binocular | [REDACTED] [REDACTED] |
| BCDVA | 4 m | Photopic (85 cd/m ²) | Monocular, Binocular | [REDACTED] [REDACTED] |

INTERMEDIATE VISUAL ACUITY AT 66 CM (MASKED PROCEDURE)

Intermediate visual acuity at 66 cm (including low contrast at 25%) will be measured under photopic conditions (85 cd/m², 80-110 cd/m² acceptable) [REDACTED] at a test distance of 66 cm. Instructions for using the [REDACTED] are detailed in **Appendix E** and for intermediate visual acuity testing in **Appendix G**.

The following visual acuity measurements are to be performed per the visit schedule in **Appendix A**:

| Test | Test Distance | Illumination | Type of Testing | [REDACTED] |
|------------|---------------|----------------------------------|----------------------|------------|
| UCVA | 66 cm | Photopic (85 cd/m ²) | Binocular | [REDACTED] |
| DCVA | 66 cm | Photopic (85 cd/m ²) | Monocular, Binocular | [REDACTED] |
| [REDACTED] | 66 cm | Photopic (85 cd/m ²) | Binocular | [REDACTED] |

INTERMEDIATE VISUAL ACUITY AT 50 CM (MASKED PROCEDURE)

Intermediate visual acuity at 50 cm will be measured under photopic conditions (85 cd/m², 80-110 cd/m² acceptable) [REDACTED] at a test distance of 50 cm. Instructions for using [REDACTED] are detailed in **Appendix E** and for intermediate visual acuity testing in **Appendix H**.

The following visual acuity measurements are to be performed per the visit schedule in **Appendix A**:

| Test | Test Distance | Illumination | Type of Testing | [REDACTED] |
|------|---------------|----------------------------------|----------------------|------------|
| UCVA | 50 cm | Photopic (85 cd/m ²) | Binocular | [REDACTED] |
| DCVA | 50 cm | Photopic (85 cd/m ²) | Monocular, Binocular | [REDACTED] |

NEAR VISUAL ACUITY AT 40 CM (MASKED PROCEDURE)

Near visual acuity will be measured under photopic conditions (85 cd/m², 80-110 cd/m² acceptable) [REDACTED] at a test distance of 40 cm. Instructions for [REDACTED] are detailed in **Appendix E** and for near visual acuity testing in **Appendix I**.

The following visual acuity measurements are to be performed per the visit schedule in **Appendix A:**

| Test | Test Distance | Illumination | Type of Testing | [REDACTED] |
|------|---------------|----------------------------------|----------------------|------------|
| UCVA | 40 cm | Photopic (85 cd/m ²) | Binocular | [REDACTED] |
| DCVA | 40 cm | Photopic (85 cd/m ²) | Monocular, Binocular | [REDACTED] |

[REDACTED]

[REDACTED]

[REDACTED]

[REDACTED]

[REDACTED]

[REDACTED]

[REDACTED]

[REDACTED]

[REDACTED]

[REDACTED]

[REDACTED]

[REDACTED]

| | | | | |
|------------|------------|------------|------------|------------|
| [REDACTED] | [REDACTED] | [REDACTED] | [REDACTED] | [REDACTED] |
| [REDACTED] | [REDACTED] | [REDACTED] | [REDACTED] | [REDACTED] |

[REDACTED]

[REDACTED]

[REDACTED]

[REDACTED]

[REDACTED]

[REDACTED]

[REDACTED]

[REDACTED]

[REDACTED]

[REDACTED]

[REDACTED]

[REDACTED]

[REDACTED]

BIOMICROSCOPIC SLIT-LAMP EXAM

A biomicroscopic slit-lamp exam must be performed at each postoperative visit to determine the presence or absence of any medical or lens findings, complications, or adverse events. IOL decentration and tilt are to be determined subjectively. The center of the lens relative to the pupil can be used to determine IOL decentration. Note that the pupil center may not always be aligned with the visual axis of the eye; therefore, the investigator should consider deviations in pupil center from visual axis when reporting IOL decentration.

Findings of aqueous cells and flare, corneal edema, posterior capsule striae (wrinkles), posterior capsular opacification and IOL glistenings are to be rated using standardized grading scales of 0 to +4 (0 = none, +4 = severe) during the slit-lamp biomicroscopy. The specific grading scales are provided in **Appendix L**.

ND: YAG CAPSULOTOMY

[REDACTED]

FUNDUS EXAM

A fundus exam is to be performed at the 6-month visit to evaluate retinal status and fundus visualization. [REDACTED]

[REDACTED]

[REDACTED] The same fundus examination method that was used preoperatively should be used for the 6-month study visit.

INTRAOCULAR PRESSURE

Intraocular pressure (IOP) is to be measured using the investigator’s usual method. It is recommended that the same method be used for all study subjects at the site for the duration of the study.

KERATOMETRY

[REDACTED]

OCULAR SYMPTOMS (NON-DIRECTED; SPONTANEOUS)

Subjective ocular symptoms are to be assessed at each postoperative visit [REDACTED]

MEDICATIONS

Postoperative ocular medications should be used as is customary for each investigator and recorded in the source document for each subject. Postoperative medications related to surgery, adverse events and serious adverse events will be recorded on a medication log CRF as applicable.

ADVERSE EVENTS

Subjects should be assessed at each visit for occurrence of and/or change in status of any adverse events, particularly serious and/or device-related adverse events. See Section 11.0, Adverse Events, for further information.

QUESTIONNAIRES

[REDACTED]

- 1) [REDACTED]
- [REDACTED]
- [REDACTED]
- [REDACTED]

[REDACTED]

Testing Equipment:

All visual acuities, as well as defocus measurements, will be performed using the [REDACTED]

[REDACTED]

This system provides a descending LogMAR chart [REDACTED]

[REDACTED] for visual acuity testing at [REDACTED]

[REDACTED]

[REDACTED]

[REDACTED]

10.8 EXIT OF SUBJECTS

An Exit CRF will be completed for all subjects, either when they complete the study or if they exit early.

It is the responsibility of the investigator to provide complete follow-up data to JJSV for each subject, and every attempt should be made to gather that complete follow-up data for all subjects enrolled, as missing data can have a negative effect on the study results. Patients who would be traveling, relocating or otherwise unavailable for postoperative follow-up visits should not be enrolled in this clinical study.

A subject will be considered a "screen failure" if he/she does not meet the eligibility criteria or does not receive study treatment. Reasons may include: the planned implant being aborted due to surgical complications, the subject withdrawing consent prior to treatment or the subject died prior to treatment.

Subjects will be "discontinued" from the study if one study lens (if implanted unilaterally) or both study lenses (if implanted bilaterally) are removed or if the subject dies.

If a subject receives at least one study lens, he/she is to be followed according to the schedule in Table 2 (Section 10.2) for visit windows.

Subjects will be considered "lost-to-follow-up" from the study only if irretrievably lost for unavoidable reasons such as: subject moved/unable to locate, subject ill/unable to travel, subject uncooperative/refuses further study participation. In the event of subject relocation, effort must be made by the investigator to secure follow-up information (i.e., slit-lamp findings and general visual acuity, etc.) from the subject's new physician. If a subject is exited early from the study, the investigator must indicate the reason for study exit on the CRF. In the event of a lens removal or other serious adverse event, the subject may be exited from the study; however, effort must be made by the investigator to follow the subject until resolution of the adverse event before exiting the subject from the study.

[REDACTED]

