10.3 PREOPERATIVE PROCEDURES

All subjects treated in the study must sign the current IRB-approved informed consent form and meet the eligibility criteria. The informed consent form must be signed before any study-specific examinations are performed, and this must be documented in the source documents. An Authorization for Use/Disclosure of Health Information Form (HIPAA authorization) or similar medical treatment privacy law documentation must also be signed.

[REDACTED]

[REDACTED]
 [REDACTED]
 [REDACTED] If a test/exam is required by the protocol but is not part of the routine testing the investigator performs for the cataract evaluation, that test/exam is considered to be study-specific and is not to be done until after the informed consent form has been signed by the subject. Following the informed consent process, completion of the preoperative study exam and determination that the subject meets all of the required entrance criteria (including lens power determination), the subject may be randomized and scheduled for surgery.

As the Informed Consent Form is signed at the beginning of the preoperative study exam, some subjects may not qualify after study-specific testing is performed. Subjects will be considered screen-failures if they do not qualify, or if they qualify but decide not to participate further in the study, or if they decide not to proceed with surgery. These subjects will be exited from the study.

Preoperative testing to be performed for each eye includes the following:

POTENTIAL DISTANCE VISUAL ACUITY

The subject must be capable of achieving Snellen 20/30 or better best-corrected distance vision in each eye after cataract extraction and IOL implantation. [REDACTED]
 [REDACTED]
 [REDACTED]
 [REDACTED]

BEST-CORRECTED DISTANCE VISUAL ACUITY AND MANIFEST REFRACTION

Preoperative manifest refraction is required. Monocular, best-corrected distance visual acuity (BCDVA) is to be measured using a standard Snellen chart or equivalent and must be Snellen 20/40 or worse, with or without a glare source.

KERATOMETRY

Predicted postoperative corneal astigmatism, as measured by keratometry, should be less than 1.00 D. No irregular astigmatism should be present preoperatively. Postoperative astigmatism can be surgically managed to be less than 1 D in each eye.

CONTACT LENS WEAR AND CORNEAL STABILITY

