1.3 RANDOMIZATION AND MASKING

A randomization list stratified by investigational sites was created by a JJSV biostatistician who is independent and not involved in the study activities. Subjects will be randomized to TECNIS Eyhance IOL or the control IOL in 1:1 ratio. Unmasked study personnel at the site will be trained to the randomization process through the EDC system and will randomize subjects after the subject has signed the informed consent form, has met all eligibility criteria and the investigator has documented which eye will be the first implanted.

Recommended steps to maintain masking include ensuring that all items pertaining to lens group assignment and lens implantation records are kept separately from all other study documents and subject medical records until after completion of the final study visit.

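### Does calling an aborted implant a screen failure (Protocol 10.8) hide exits that happen after randomisation?

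*Protocol*

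**What the plan says.** Both documents put randomisation ahead of surgery. Under Protocol 10.3, once the preoperative exam is finished and eligibility is confirmed, "the subject may be randomized and scheduled for surgery". SAP 1.3 has unmasked site staff who "will randomize subjects after the subject has signed the informed consent form, has met all eligibility criteria", with the choice of first eye already documented.

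Protocol 10.6 foresees operations that end without a lens: "In the event of capsular bag or zonular rupture, the lens should not be implanted if the complication may result in lens instability".

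Protocol 10.8 then defines a screen failure as a subject who does not meet the criteria "or does not receive study treatment. Reasons may include: the planned implant being aborted due to surgical complications". The other reasons it names are withdrawal of consent and death, each before treatment. The same section adds two rules that bear on the point. First, "If a subject receives at least one study lens, he/she is to be followed according to the schedule in Table 2". Second, "An Exit CRF will be completed for all subjects, either when they complete the study or if they exit early", and for an early exit the investigator must state the reason on that form.

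Protocol 10.3 has its own version of the label. It covers subjects who do not qualify, who qualify but choose not to go on, "or if they decide not to proceed with surgery. These subjects will be exited from the study". It does not mention an implant aborted in surgery.

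SAP 3.1 tabulates enrolment by site and accountability by scheduled visit, and says all summaries are by group. The group it names is OVD, which is not a group in this trial; SAP section 4 uses IOL group.

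**The concern.** A screen failure is normally someone who leaves before assignment and so belongs to neither arm. Here the label also covers people who were assigned to a lens, went to surgery and came out without it. If both kinds are reported in one row, a reader cannot see how many randomised subjects were lost at surgery, or from which arm.

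That split could be informative. Protocol 10.6 leaves implantation after a complication to the investigator's discretion. The visible masking text covers subjects and vision-testing technicians and does not mention the surgeon. Delivery format can also differ between arms: the control may be the folded ZCB00 or the preloaded DCB00, while the test lens comes with the Simplicity system. At stake would be a clear account of every randomised subject and, if the losses were many and lopsided, the comparability of the arms.

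**Working it through.** **1. Does the label reach randomised subjects?** Yes. The sequence is consent, preoperative exam, eligibility, randomisation, surgery. An implant aborted during surgery is necessarily a post-randomisation event, and no redaction alters that.

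**2. How many could be affected?** Only subjects with no study lens in either eye. Anyone with one study lens stays on the visit schedule under 10.8, so an implant aborted in the second eye after a successful first falls outside the label.

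**3. Is the information lost?** Take one such subject through the records:

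| Item needed | Where it is held |
|---|---|
| Assigned lens | Randomisation code in the EDC (Protocol 10.4) |
| Fact of exit | Exit CRF for every subject (Protocol 10.8) |
| Reason for exit | Required on the CRF for early exits (Protocol 10.8) |
| Adverse events | Reported whatever their severity or cause (Protocol 11.3) and followed up (Protocol 11.5) |

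An aborted implant is therefore distinguishable from a failed eligibility check, and its arm is known.

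**4. Does the plan commit to a pooled count?** No visible text does. SAP 3.1 points the other way once OVD is read as IOL. The text that would settle the matter cannot be read: Protocol 20.1 and 20.2 (analysis populations and missing data), parts of 10.4, 10.6 and 10.8, and the contents of SAP Appendix I, which SAP 2.3 says lists the tables and their populations.

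**5. Size for the efficacy tests.** The sample-size figures reproduce. Enrolment: 200 × 1.10 = 220, the stated number (200/0.90 = 222.2, so 223, is close). Power, from Protocol 20.7, with n per arm:

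λ = δ / (σ√(2/n)), power = P(T > t) with T noncentral t on 2n − 2 degrees of freedom and noncentrality λ, and t the critical value.

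- DCVA66: δ = 0.8 line, σ = 1.6 lines, one-sided 0.025. At n = 100, λ = 0.8/(1.6 × 0.1414) = 3.54, power 94.0% (stated: over 90%).
- BCDVA: margin 1 line, σ = 1.2 lines, no true difference, one-sided 0.05. At n = 100, λ = 1/(1.2 × 0.1414) = 5.89, power above 99.9% (stated: over 90%).

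| n per arm | DCVA66 power | BCDVA power |
|---|---|---|
| 105 | 95.0% | >99.9% |
| 100 | 94.0% | >99.9% |
| 95 | 92.9% | >99.9% |
| 90 | 91.6% | >99.9% |

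The planned 90% holds throughout this range.

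**6. What a pooled count could conceal.** The documents give no rate of aborted implants, so this is an assumption only: six in all, with 110 randomised per arm. Two-sided Fisher tests give p = 1.00 for 3 v 3 (2.7% each), p = 0.21 for 5 v 1 (4.5% v 0.9%) and p = 0.03 for 6 v 0 (5.5% v 0%). With five in all, even 5 v 0 gives p = 0.06. Of these splits, only the wholly one-sided 6 v 0 falls below 0.05.

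**The case for a change.** The best case for amending the text is that the definition itself is in plain view and mixes two kinds of exit, whatever the redacted parts say. SAP 3.1 names available eyes and missing and active subjects, but shows no line for those randomised and not implanted. SAP 7.4 confines its cumulative event tables to implanted eyes, so an operative event in an eye left without a study lens might not appear there. The implant decision may also be made with the assigned lens known. Correcting the wording would be cheap.

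Most of this is factually right, and the terminology is untidy. Two things are missing. First, no by-arm reporting gap is shown: the data exist, the visible summaries are by group, and a row that may sit in an unseen table listing cannot be called absent. Second, no planned result would move. SAP 7.4 concerns non-serious events unrelated to the device. Tabulating implanted eyes is a defensible choice for lens outcomes, and a subject exited for a serious event is followed until its outcome is known (Protocol 11.5). The 10.3 limb is weaker still. Its sentence sits in a paragraph about subjects who may fail study-specific testing, and it reaches randomised subjects only by implication.

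**Conclusion.** The observation is correct and the consequence is not established. Protocol 10.8 uses one label for exits before and after randomisation, but the exit reason and assigned lens are both recorded, so whoever builds the disposition table can separate the two without new wording in the plan. Separating them is ordinary practice in accounting for randomised subjects.

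Relabelling would change no estimate, test, success criterion or stated figure. Loss of 5 or 10 subjects per arm from 100 leaves DCVA66 power at 92.9% or 91.6%, and BCDVA power does not move visibly.

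This rests on two assumptions: that OVD in SAP 3.1 is a slip for IOL, and that aborted first implants with no later study lens are few, since the documents give no rate. It makes no claim about which analysis sets include these subjects, because that text is not available. If the full text showed a single pooled screen-failure row with no split by arm, the point would be worth raising again, as a matter of reporting.

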10.9 UNSCHEDULED VISITS

During the study period, if a non-protocol-required visit is done for the purpose of medically-indicated follow-up for a study eye, data from this visit should be reported using the Unscheduled Visit CRF. The need for unscheduled visits is at the investigator’s discretion. Specific examinations to be performed at unscheduled visits are also at the discretion of the investigator (based on the reason for the unscheduled visit) and data are to be recorded in the appropriate section of the CRF.

Data to be collected may include:

- Snellen manifest refraction
- Uncorrected and best-corrected distance visual acuity using a Snellen chart
- Intraocular pressure
- Slit-lamp examination for medical and/or lens findings
- Fundus exam
- Ocular symptoms
- Adverse events
- Medications

[REDACTED]

[REDACTED]

Conditions found postoperatively, but previously documented at the preoperative visit, do not trigger an unscheduled visit report. However, if the severity of the condition increases from the preoperative visit, an Unscheduled Visit CRF is needed.

[REDACTED]

[REDACTED]

[REDACTED]

[REDACTED]

[REDACTED]

[REDACTED]

[REDACTED]

[REDACTED]

[REDACTED]

